4.2.10. Visit Windows

Any clinical domains that are displayed by visit will be shown by nominal study visit.

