- Video-EEG (8–24 hours in duration).
- Clinical laboratory samples (blood and urine [if possible]) for:
 - Serum biochemistry.
 - Hematology.
 - Urinalysis.
- CGIC.
- PGIC.
- Caregiver diary review for:
 - Spasm/seizure information.
 - IMP usage.
 - Changes in concomitant AEDs.
 - Usage of rescue medication.
 - AEs.
- AEs.
- IMP compliance.
- IMP dispensing.

Visit 7 (Day 43 [±3 Days]); Visit 8 (Day 71 [±3 Days]); Visit 9 (Day 127 [±7 Days]); Visit 10 (Day 211 [±7 Days]); Visit 11 (Day 295 [±7 Days]); Visit 12 (Day 379 [±7 Days]): End of OLE Treatment/Withdrawal

The following will be collected/assessed at each of the above visits:

• Concomitant medication review.

EudraCT Number: 2015-004904-50

Protocol V3 20Sep16

Procedures (continued)

- Physical examination (including length [height], body weight, and head circumference).
- Vital signs (including supine blood pressure).
- ECG.
- Clinical laboratory samples (blood and urine [if possible]) for:
 - Serum biochemistry.
 - Hematology.
 - Urinalysis.
- CGIC.
- PGIC.
- Caregiver diary review for:
 - Spasm/seizure information.
 - IMP usage.
 - Changes in concomitant AEDs.
 - Usage of rescue medication.
 - AEs.
- AEs.
- IMP compliance.
- IMP dispensing (only if necessary at Visit 12).

The following will also be collected/assessed in addition to the above:

- Video-EEG (8–24 hours in duration) (Visits 7 and 9–12, or on withdrawal).
- Vineland-II (Visits 10 and 12, or on withdrawal).

Taper Period (10 Days)

Following end of treatment, discontinuation of IMP, or withdrawal, all patients will taper IMP (unless continued dosing is not possible due to an AE).

End of Taper Period Visit (+3 Days)

The following will be collected/assessed:

- Concomitant medication review.
- Physical examination (including length [height], body weight, and head circumference).
- Vital signs (including supine blood pressure).
- ECG.
- Clinical laboratory samples (blood and urine [if possible]) for:
 - Serum biochemistry.
 - Hematology.
 - Urinalysis.

Procedures (continued)

- Caregiver diary review for:
 - Spasm/seizure information.
 - IMP usage.
 - Changes in concomitant AEDs.
 - Usage of rescue medication.
 - AEs.
- AEs.
- IMP compliance.

Safety Follow-up Period (4 Weeks)

Following end of dosing (including taper period), all patients will commence a 4-week safety follow-up period, which includes weekly safety telephone calls followed by a safety follow-up visit.

Weekly Safety Telephone Calls (±3 Days)

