9.1.1.5 Visit 4 (Day 15 [+3 Days]): End of Pilot or Pivotal Phase/Withdrawal

This visit will occur 14 (+3) days after Visit 2 or earlier if the patient withdraws from the pilot or pivotal phase of the trial. The following will be collected/assessed:

- Concomitant medication review (Section 9.2.5).
- Physical examination (Section 9.2.6).
- Vital signs (Section 9.2.7).
- ECG (prior to the day's first dose of IMP; Section 9.2.8).
- Video-EEG (Section 9.2.9).
- Clinical laboratory samples (blood and urine [if possible]; Section 9.2.10) for:
 - Serum biochemistry.
 - Hematology.
 - Urinalysis.
- **Pivotal phase only**: PK blood sampling (prior to the day's first dose of IMP, provided the risk/benefit outcome is favorable in the investigator's opinion; Section 9.2.11).
- CGIC (Section 9.2.12.1).

- PGIC (Section 9.2.12.2).
- Caregiver diary review (Section 9.2.13) for:
 - Spasm/seizure information.
 - IMP usage.
 - Changes in concomitant AEDs.
 - Usage of rescue medication.
 - AEs.
- AEs (Section 12).

Patients will take their IMP in the clinic with an additional ECG assessment between 3 and 5 hours postdose (Section 9.2.8). For patients involved in the pivotal phase of the trial, a further PK blood sample will be taken, provided the risk/benefit outcome is favorable in the investigator's opinion (Section 9.2.11). If PK blood samples are collected, the investigator must note the sampling times and the dosing times of the IMP and of any concomitant AEDs taken that day and the previous day. All IMP will be collected and compliance reviewed.

Patients who have successfully completed the pilot or pivotal phase will have the opportunity to receive GWP42003-P during the subsequent OLE phase at Visit 4. Patients from the pilot phase who enter the OLE phase will remain at the target dose which was reached during the pilot phase. Patients from the pivotal phase who enter the OLE phase will receive sufficient blinded IMP for tapering along with sufficient OLE IMP (GWP42003-P) for simultaneous titration and subsequent dosing for 2 weeks. All patients in the pivotal phase who enter the OLE phase will transition to the target dose of GWP42003-P (in a blinded manner; Section 8.1.2) and may continue at this dose, or the highest tolerated dose up to 40 mg/kg/day, for the remainder of the OLE phase. Following Visit 4, daily safety checks will be made during the first week of GWP42003-P dosing.

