9.1.2 Open-label Extension Phase

The OLE phase will last for a maximum of 1 year.

During the OLE phase, GWP42003-P may be discontinued by the investigator if:

EudraCT Number: 2015-004904-50

Protocol V3 20Sep16

• The patient has become spasm-free, as determined by clinical assessment by the investigator.

OR

• The patient is not perceived to be receiving any benefit from GWP42003-P, as determined by clinical assessment by the investigator.

For any patients who have their IMP discontinued by the investigator, the IVRS/IWRS will be contacted to confirm IMP discontinuation. All patients should commence the taper period, if possible (Section 9.1.3), and sufficient IMP will be dispensed if required.

If the investigator decides to discontinue GWP42003-P following resolution of spasms, the parent(s)/legal representative will be encouraged to allow the patient to remain in the trial to complete the remaining assessments. The investigator must contact the GW medical monitor to discuss the discontinuation process, including the subsequent assessments to be conducted.

If the investigator decides to discontinue GWP42003-P because the patient is not perceived to be receiving any benefit from GWP42003-P, the patient will **not** be asked to complete the remaining trial assessments and will be withdrawn from the trial as per Section 10 (withdrawal to be registered in the IVRS/IWRS).

Patients who have not demonstrated complete resolution of spasms but are perceived to be receiving some benefit from GWP42003-P may remain in the OLE and receive other concomitant medications during the OLE phase. The option of withdrawal from the trial will be discussed with the caregiver at each visit.

In cases of relapse, patients may restart IMP only if ALL of the following criteria are fulfilled:

- The patient had their IMP discontinued by the investigator due to resolution of spasms.
- The patient has remained in the trial to complete the remaining assessments.
- The decision to restart IMP is discussed with the GW medical monitor.

The IVRS/IWRS will then be contacted to confirm restart of IMP. Patients restarting IMP will re-titrate to their target dose of GWP42003-P and may continue at this dose, or the highest tolerated dose up to 40 mg/kg/day, for the remainder of the OLE phase. The next scheduled clinic visit will then be performed according to the Schedule of Assessments (APPENDIX 1).

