9.1.2.9 Visit 12 (Day 379 [±7 Days]): End of OLE Treatment/Withdrawal

This visit will occur 378 (\pm 7) days after Visit 2 or earlier if the patient withdraws from the OLE phase of the trial. The following will be collected/assessed:

- Concomitant medication review (Section 9.2.5).
- Physical examination (Section 9.2.6).
- Vital signs (Section 9.2.7).
- ECG (Section 9.2.8).
- Video-EEG (Section 9.2.9).
- Clinical laboratory samples (blood and urine [if possible]; Section 9.2.10) for:
 - Serum biochemistry.
 - Hematology.
 - Urinalysis.
- CGIC (Section 9.2.12.1).
- PGIC (Section 9.2.12.2).
- Vineland-II (Section 9.2.12.3).
- Caregiver diary review (Section 9.2.13) for:
 - Spasm/seizure information.
 - IMP usage.
 - Changes in concomitant AEDs.
 - Usage of rescue medication.
 - AEs.
- AEs (Section 12).

All IMP will be collected and compliance reviewed. For patients who withdraw early, the IVRS/IWRS will be contacted to confirm withdrawal from the trial. All

patients should commence the taper period, if possible (Section 9.1.3), and sufficient IMP will be dispensed.

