- If a patient is not showing evidence of benefit during the OLE phase (the option of withdrawing from the trial will be discussed with the caregiver at each visit).
- Patient/caregiver non-compliance.
- AE (including clinically significant laboratory result) which, in the opinion of the investigator, would compromise the continued safe participation of the patient in the trial.

Should a patient's parent(s)/legal representative request or decide to withdraw the patient from the trial, all efforts must be made to complete and report the observations as thoroughly as possible up to the date of withdrawal. Patients who are withdrawn should have their dose of IMP tapered gradually (10% each day) over a period of 10 days, beginning at the time the decision is made to discontinue. In some cases, tapering the dose of IMP may be inadvisable (e.g., continued dosing is not possible due to an AE). The decision on whether or not to taper IMP will be left to the investigator's clinical judgment. All assessments required at Visit 4 (end of pilot or pivotal phase/withdrawal) or Visit 12 (end of OLE treatment/withdrawal), as appropriate, should be conducted if possible. If the tapered dose is administered, caregivers should continue to complete the paper diary and return for the end of taper period visit, if possible. For patients who begin to taper IMP but are subsequently withdrawn, the end of taper period visit assessments (including ECG and clinical laboratory sampling) should be conducted, if possible; this visit should occur on the final day of dosing or as soon as possible after this date. Patients who are withdrawn due to an AE should be followed up according to Section 12.6. All information should be reported on the applicable CRF pages (refer to Section 9.2). Wherever possible, a safety follow-up visit should take place 28 days after the last dose of IMP (refer to Section 9.1.4.2). If the parent(s)/legal representative of withdrawing patients decline to give a reason for withdrawal of consent, the investigator must respect these wishes.

EudraCT Number: 2015-004904-50

Protocol V3 20Sep16

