2.6. Secondary Endpoints

2.6.1. *Pilot Phase*

For the pilot phase, the following secondary endpoints will be analyzed descriptively only:

- The number and proportion of patients who are free of clinical spasms, as observed on video-EEG at the end of the treatment period.
- The number and proportion of patients who have resolution of hypsarrhythmia, as observed on video-EEG at the end of the treatment period.
- Changes in spasms and seizure subtypes by caregiver observation during the treatment period.
- Time to cessation of spasms during the treatment period, as determined by caregiver diaries.
- CGIC.
- PGIC.

2.6.2. *OLE Phase*

For the OLE phase, the following secondary endpoints will be analyzed descriptively only:

- The number and proportion of patients who are free of clinical spasms, as observed on video-EEG at the end of the treatment period.
- The number and proportion of patients who have resolution of hypsarrhythmia as, observed on video-EEG at the end of the treatment period.
- Changes in spasms and seizure subtypes by caregiver observation during the treatment period.
- Time to cessation of spasms during the treatment period, as determined by caregiver diaries.
- The number and proportion of patients who are free of spasms and have resolution of hypsarrhythmia, as determined by video-EEG after 3, 6, 9 and 12 months of treatment.

GW Research Ltd Study Code: GWEP15100 EudraCT Number: 2015-004904-50

25SEP2019

- The number and proportion of responders with relapse of spasms, and the time to relapse, as determined by caregiver diaries.
- Changes from baseline in length (height), body weight, and head circumference.
- CGIC.
- PGIC.
- Change from baseline in Vineland-II score.

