4.8.4. Vital Signs and Physical Examinations

Vital signs measurements (systolic and diastolic blood pressure, pulse rate, body temperature, respiratory rate, height, weight, BMI, and head circumference), taken in a supine position at rest for 5 minutes, will be completed alongside the physical examination.

Physical examinations will include length (height), body weight, and head circumference measurements.

Vital signs and physical examination data will be summarized at screening, baseline, and at each time point during the treatment period using descriptive statistics. Changes in the vital signs from baseline to end of treatment will also be summarized.

All vital sign and physical examination measurements will be presented in data listings.

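### Under the SAP's nominal-visit rule, early OLE withdrawal values enter the Visit 12 row of the growth and Vineland-II tables, and SAP 4.7 does not carry out the OLE composite endpoint listed in SAP 2.6.2

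*SAP*

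**What the plan says.** **Visits.** The protocol gives the last visit of each phase two functions. Visit 4 falls 14 (+3) days after Visit 2 "or earlier if the patient withdraws from the pilot or pivotal phase of the trial" (Protocol 9.1.1.5). Visit 12 falls 378 (±7) "days after Visit 2 or earlier if the patient withdraws from the OLE phase of the trial" (Protocol 9.1.2.9). For withdrawn patients, Protocol 10 asks that "All assessments required at Visit 4 (end of pilot or pivotal phase/withdrawal) or Visit 12 (end of OLE treatment/withdrawal), as appropriate" be done where possible. The schedule of assessments has columns for the end of taper and for safety follow-up, but none for early termination. Leaving the OLE is a standing option: "The option of withdrawal from the trial will be discussed with the caregiver at each visit" (Protocol 9.1.2).

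**Display rule.** SAP 4.2.10, headed Visit Windows, contains one sentence: "Any clinical domains that are displayed by visit will be shown by nominal study visit". Nothing else in the SAP text or its table list separates withdrawal records.

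**Outputs shown by visit.**
- Vineland-II: the protocol synopsis times it as "Vineland-II (Visits 10 and 12, or on withdrawal"). SAP 4.7.3.4 scores it as a raw item sum and shows it by visit for the OLE only.
- Growth: SAP 2.6.2 lists "Changes from baseline in length (height), body weight, and head circumference" as an OLE secondary endpoint, with no time point. SAP 4.8.4 says: "Vital signs and physical examination data will be summarized at screening, baseline, and at each time point during the treatment period using descriptive statistics". It names height, weight and head circumference under both vital signs and physical examination. Change by visit comes from the titles of Tables 14.1 and 14.2.
- CGIC and PGIC: by visit (SAP 4.7.3.2 and 4.7.3.3).

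**OLE composite.** SAP 2.6.2 and Protocol 13.6.3.3 list the proportion who are spasm-free with hypsarrhythmia resolved at 3, 6, 9 and 12 months. SAP 4.7.1.1 promises a responder summary for each phase but defines a responder only at the end of 2 weeks. Table 8.1.2 nevertheless reports OLE responders. SAP 4.7.2.1 takes the spasm component at all four months; SAP 4.7.2.2 takes hypsarrhythmia at 3, 6 and 12 only.

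**The concern.** A Visit 12 row reads as a one-year result. If it also holds assessments from patients who left after a few weeks, its mean change in weight, length, head circumference or Vineland-II can be low because follow-up was short, not because the children grew or developed slowly. A reader of the table cannot separate the two.

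The mixing would also tend to be informative. Under Protocol 9.1.2, patients taken off drug because they are spasm-free are encouraged to stay for the remaining assessments. Those taken off for lack of perceived benefit are withdrawn. Early records under the Visit 12 label would therefore come disproportionately from patients judged not to benefit, measured at a younger age.

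For the composite, a programmer following SAP 4.7 has no definition for an OLE responder table at months 3, 6, 9 and 12, and would produce no month-9 hypsarrhythmia result. SAP 1.1 undertakes to outline departures from the protocol's planned objectives, but SAP 5 records only the dropped pivotal phase.

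**Working it through.** **How far apart the pooled records can be.** Days after Visit 2 = study day − 1. This reproduces the protocol's own offsets: 15 − 1 = 14 and 379 − 1 = 378.
- On-schedule Visit 12 window: 379 − 7 = Day 372 to 379 + 7 = Day 386.
- Earliest OLE withdrawal record, the day after Visit 4: Day 16. That is 372 − 16 = 356 days before the window opens and 379 − 16 = 363 days before the target day.
- Visit 4: the earliest record is Day 2, so at most 15 − 2 = 13 days early. The scope for mixing there is much smaller. Vineland-II is not done at Visit 4, so it is exposed only at Visit 12.

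**Weight of one record.** SAP 4.1 gives 9 pilot patients and SAP 5 confirms that no others were included, so the OLE has at most 9. One record is at least 1/9 = 11% of the row.

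**Illustration.** Assumed: all 9 are in the Visit 12 row, gain is linear and equal across patients, and withdrawals fall on scheduled visit days. The share of planned follow-up completed is f = (day − 1)/378. The fall in the row's mean change per withdrawal, as a fraction of the one-year gain, is (1 − f)/9.

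| Leaves at | Day | f | (1 − f)/9 |
|---|---|---|---|
| Visit 5 | 19 | 0.048 | 0.106 |
| Visit 6 | 29 | 0.074 | 0.103 |
| Visit 7 | 43 | 0.111 | 0.099 |
| Visit 8 | 71 | 0.185 | 0.091 |
| Visit 9 | 127 | 0.333 | 0.074 |
| Visit 10 | 211 | 0.556 | 0.049 |
| Visit 11 | 295 | 0.778 | 0.025 |

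The mean follow-up in the row with k withdrawals on day d is ((9 − k) × 378 + k(d − 1))/9. For d from 43 to 211:
- k = 1: (3024 + 42)/9 = 341 to (3024 + 210)/9 = 359 days.
- k = 2: (2646 + 84)/9 = 303 to (2646 + 420)/9 = 341 days.
- k = 4: (1890 + 168)/9 = 229 to (1890 + 840)/9 = 303 days.

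The values of k are assumed; the documents give no withdrawal count.

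**Months and visits for the composite.** With a month of 30.44 days, Visits 9, 10, 11 and 12 (Days 127, 211, 295 and 379) fall at (day − 1)/30.44 = 4.1, 6.9, 9.7 and 12.4 months from first dose. From Day 15, the start of the OLE, (day − 15)/30.44 = 3.7, 6.4, 9.2 and 12.0 months. These four visits are the evident match for 3, 6, 9 and 12 months, and the fit is closer from OLE start. No text states the match or the origin.

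**The case against.** The strongest reply is that the mixing is inferred. Table shells and database visit labels are not in the documents, and the synopsis wording for Vineland-II names withdrawal alongside Visit 12 as if it were a separate occasion. A separate row could still be programmed. That is fair, and it limits the claim to what the plan specifies. But Protocol 9.1.2.9 and 10 fold withdrawal into Visit 12, and the only SAP display rule is the nominal visit.

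Second, the listings give visit dates, disposition and values for every patient, and Protocol 13.4 requires n for continuous summaries, so a rise in n at Visit 12 would hint at pooling. This allows a partial check. It does not show what the pooled values were, and a patient who leaves between Visits 11 and 12 causes no such rise.

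Third, a reader might infer that CGIC and PGIC are distorted in the same way. The documents do not support that. Both compare the patient's condition now with that before treatment, so the elapsed-time argument does not carry over. A last on-treatment rating has a reasonable place at an end-of-treatment visit.

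Fourth, a separate early-termination row may hold one or two patients, which makes its mean and standard deviation almost meaningless, and what remains is a completers-only row. Both points stand and are costs of the fix.

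Fifth, the composite gap looks like drafting error: SAP 2.6.2 keeps all four months and Table 8.1.2 is planned. That is likely, but the section that governs the analysis still does not say what to compute.

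**Conclusion.** Both parts hold on the text and should be corrected, with limited consequences.

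1. As written, the plan places early OLE withdrawal values in the Visit 12 row. The effect is greatest for growth (Table 14.2, and Table 14.1 if it carries the same measures) and for the raw-sum Vineland-II. It is smaller for CGIC and PGIC and for the Visit 4 rows.
2. SAP 4.7 does not carry out the OLE composite listed in SAP 2.6.2 and Protocol 13.6.3.3, omits month 9 for hypsarrhythmia, and does not tie months to visits.

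The illustrated size, 2.5% to 10.6% of the one-year gain per withdrawal, rests on 9 patients in the row and equal linear gain.

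A reader might go further and conclude that the reported growth or Vineland-II results are biased. The documents do not support this: they give no withdrawal count, so the distortion may be nil. Nor does the point threaten any error rate, because SAP 4.2.1 rules out formal hypothesis testing. Nor does it follow that withdrawal assessments should be discarded: they remain appropriate for endpoints defined at the end of treatment. Finally, the gap in SAP 4.7 does not show that the composite was dropped on purpose.

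**What to change.** (a) In SAP 4.2.10, state that assessments done because of early withdrawal appear in a separate early-termination row, with n and the range of study days. Place it beside the on-schedule Visit 12 row, and beside the Visit 4 row where relevant. Apply this to Vineland-II and to growth in Tables 14.1 and 14.2 and, for consistency, to the other by-visit tables. Add a footnote that the on-schedule Visit 12 row is completers only and may favour the drug, because patients without perceived benefit may be withdrawn. Keep withdrawal values in the end-of-treatment endpoints.

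(b) In SAP 4.7, define the OLE composite responder at Visits 9, 10, 11 and 12, label these by study day (127, 211, 295 and 379), and restore month 9 in SAP 4.7.2.2.

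Cost: SAP text and table shells only. No new data are needed, because visit dates and withdrawal reasons are already to be listed. The price is smaller, completers-only on-schedule rows, and early-termination rows with very few patients. The two must be read together.

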4.3. Interim Analyses

An interim analysis is not planned for this study.

4.4. Subject Disposition

All patients (enrolled, screened, treated, entering the OLE, prematurely terminating IMP) will be accounted for in the enrollment and disposition summary tables.

A tabulation of subject disposition will be displayed, including the number enrolled, the number screened, reasons for screen failure, the number randomized, the number that completed the pilot phase and the number that entered the open label extension phase.

A listing of screen failures and a listing of study completion information, including the primary reason for study withdrawal, if applicable, will be presented by cohort and subject.

4.5. Demographic and Baseline Characteristics

Demographic data, including gestational age, birth weight, age at informed consent, sex and race, will be summarized using descriptive statistics. For continuous variables, mean, standard deviation, median, minimum, and maximum will be presented. For categorical variables, N and % will be presented.

Demographic and baseline data will also be provided in data listings by cohort and site.

4.6. Medical History

Previous and current significant non-epilepsy medical history will be summarized using System Organ Class (SOC) and Preferred Term (PT).

Non-epilepsy medical history data will also be provided in data listings by cohort and site.

